2.1 Aims and Objectives

The overarching aim of RECEDE study is to investigate the diagnostic accuracy of dual testing with stool FIT plus urine VOC compared to stool FIT alone to improve detection of SBD. If sufficiently accurate this has the potential to reduce the number colonoscopies and CTCs in those without SBD.

#### Detailed list of research objectives include:

#### Clinical

- Comparative sensitivity, specificity, negative predictive value (NPV) and positive predictive value (PPV) of (i) FIT, (ii) urine VOC and (iii) FIT plus urine VOC for detection of SBD.Developing an optimisation of sensitivity threshold for FIT, VOC and FIT + VOC when tests are either performed in parallel or sequentially as an exploratory outcome.
- Potential number of colonoscopies and CTCs avoided in those without SBD
- Survey of NHS stakeholders and policy decision makers as to acceptable sensitivity of diagnostic strategies before implementation into clinical practice. These will include members of the Cancer Alliance Network who will be asked to complete an online survey when results are available.
- Return rate of stool and urine samples

#### Economics

- Estimation of per-participant NHS & Personal Social Services (PSS) costs associated with each of the compared options (FIT plus urine VOC compared to FIT alone, as indicators for colonoscopy)
- Impact of colonoscopy and CTC on participants' health-related quality of life (colonoscopy disutility including bowel preparation).
- Number of potentially avoidable colonoscopies, CTCs and resulting savings. We will also consider opportunity benefits such as reduced waiting times for other participants
- Estimation of quality-adjusted life years (QALYs) associated with each of the compared options (FIT plus urine VOC compared to FIT alone)
- Overall cost-effectiveness of adding VOC testing in the diagnostic pathway.

All 1,915 participants clinical data and surplus samples associated metadata will be stored in the Arden Tissue Bank (hosted at UHCW) and will be made available (upon written application and approval by the TSC and Chief Investigator) for Universities, NHS and commercial researchers worldwide for further research.

#### **3 STUDY DESIGN**

This is a prospective diagnostic accuracy study to compare dual testing of stool FIT with urine VOC markers compared to single testing with FIT, in the detection of SBD – see Figure 1.

#### 4 STUDY SETTING

RECEDE will be a multicentre diagnostic accuracy study, in centres that receive referrals from primary care for those with lower gastrointestinal symptoms.

#### 5 ELIGIBILITY CRITERIA

5.1 Inclusion criteria

- All participants referred either routinely with lower gastrointestinal symptoms or urgently (fulfilling the national criteria for referral NICE NG12) for colonoscopy or CTC that is determined by their overseeing clinician
- Minimum age of 18
- Able to provide informed consent
- Have the ability to return both stool and urine samples

5.2 Exclusion criteria

- Those who are pregnant

#### **6 STUDY PROCEDURES**

Recruitment options will be tailored to the respective site either remotely or at time of clinic visit. This is shown in Appendix B Figures 1 and 2. If the clinician decides that colonoscopy or CTC is required the participant will then be invited to participate in the RECEDE study – see Figure 1.

Informed consent will be obtained and Case Report Forms (CRFs) completed and questionnaires (EQ-5D) handed out at the same time (questionnaires will only be requested at the sponsor site - UHCW). The participant will be requested to provide a stool sample from home and post for analysis, which must be at least 24 hours before starting bowel cleansing medication. Urine samples can be collected either during a clinic visit (preferential) or, if this is not possible, at home and either sent via GP courier back to the hospital or hand delivered by the participant on a future visit to the hospital that aligns with standard care at the recruiting site. Participants are requested to record date and time when samples are collected. Participants may be provided with cool bags if collecting urine from home, if participant needs to freeze their sample at home and the sample is likely to be out of the freezer for longer than 1 hour before returned to the hospital.

For stool samples, a pre-prepared stool collection kit is provided together with return envelope to be posted directly to the Rugby Bowel Cancer Screening Hub – see Figure 4A below. The kit can either be posted to participants or given directly at time of clinic visit (site dependant). Stool samples are required at least 24hrs **prior** to commencing bowel preparation for colonoscopy.

For urine samples (sample collection kit shown in Figure 4B), this can be collected either at the time of a hospital visit or at home (at least 24hrs prior bowel preparation) and kept in a freezer until returned if the sample cannot be returned the same day as it is produced. At site level, the PI may adapt based on local policy. If the sample is frozen at home by the participant, cool bags with ice blocks can be provided to maintain cold chain until deposit at the site freezer. Depending on the site, participants may have the option of returning samples to their respective GPs for transfer to the site. We will aim for the time between the sample being produced and the sample being frozen at -80°c to be <4 hours, unless the participant freezes their sample at their home first.

**Figure 4 A**: Stool FIT sampling and return kit. This is similar to that used in the bowel cancer screening programme nationally. **B**: Urine sample kit.

6.1 Screening and Recruitment

IRAS 282247\_RECEDE protocol\_v2.2\_11.02.2022 Page **21** of **50** 

Screening will be undertaken by each site once referral from primary care has been received and date of appointment in secondary care is known. An invitation letter, PIS, and consent form will then be sent or given to participants accordingly and participation will be requested in the event that the clinician organises a colonoscopy or CTC. It is important for each site to ensure that participants are approached sequentially (unless they decline) to avoid risk of bias.

Two potential pathways are highlighted in Appendix B Figure 1 and 2.

#### 6.2 Participant identification

At each site, a dedicated clinical research team member will identify potential participants through screening methods described above.

#### 6.3 Assessment for eligibility

The PI or Research/Clinical staff at each site will have oversight and confirm eligibility if referral criteria are met and participant has agreed to undergo a colonoscopy or CTC (requested by overseeing clinician).

#### 6.4 Payment

It is envisaged that recruitment can be undertaken as part of participant visit to clinic or colonoscopy. Hence no additional visits or inconvenience are anticipated for potential recruits, unless participants test CTC negative, but FIT or VOC positive. At the end of the study, this cohort (imagined to be a small percentage) will be recommended for further investigation with colonoscopy. For samples that will be posted, a pre-paid self-addressed envelope will be provided. No payment will be made to participants.

#### 6.5 Consent

It is envisaged that the PIS and invitation letter can be sent by post to the participant ahead of their colonoscopy or CTC appointment (site dependant). The study team will telephone participants after they receive this information to confirm they are interested in taking part in the study, with the study details being explained to them at this point. Verbal consent can be given and recorded at this time. Written consent only needs collecting if recruiting the participant face to face. Participants will be encouraged to ask questions and they will have the right to decline to take part in the study without giving any reasons. They will also remain free to withdraw at any time from the study. Participants will be enrolled into the study once verbal consent is given. If telephone consent is obtained, a copy of the consent form signed by the staff member obtaining consent will be sent to the participant.

If unable to get hold of a potential participant before a clinic visit, consent can be obtained from them during a pre-colonoscopy clinic visit. The PIS and invitation letter can be given to them by a research nurse on that day with the study details being explained to them at that point. Participants will still be encouraged to ask questions and have the right to decline to participate in the study at that time. If the participant agrees to participate then written consent can be recorded on that day, with the participant then becoming enrolled in the study, or they can be contacted by telephone at a later date.

The Principal Investigator (PI) retains overall responsibility for the conduct of research at their site; this includes the taking of informed consent of participants at their site. They must ensure that any person delegated responsibility to participate in the informed consent process is duly authorised, trained and competent. If verbal translation is needed, this will be via a hospital interpreter or an independent interpreter or telephone translation services where available.

#### 6.6 Follow Up

Participants referred to CTC will be followed up for a longer duration, at least 52 weeks post-CTC procedure or until the study results are un-blinded. The follow-up check is on the participant's medical records to determine if they have a lower GI diagnosis later on that was not picked up by CTC.

IRAS 282247\_RECEDE protocol\_v2.2\_11.02.2022 Page **22** of **50** 

It is anticipated that a small number of participants may return false negative results from their CTC as CTC is not able to pick up microscopic colitis, a treatable serious bowel condition. Whereas it is predicted that dual testing FIT + VOC may be able to detect if microscopic colitis is present in this population. Therefore those who return a negative CTC, but following analysis show a FIT or VOC positive result and did not have any further specialist lower GI care following checks on their medical records, will be re-contacted and recommended for further investigation with colonoscopy. The prevalence of microscopic colitis in those referred for further bowel investigation is small (<0.5%) and so we predict that this will only occur in a small number of participants.

#### 7 DATA MANAGEMENT

#### 7.1 Baseline data

This will include demographic data (age, sex, and ethnicity). Clinical data will include lifestyle and medical history, including medications. This data collection is part of standard care for those suspected of SBD but may vary according to local site procedures.

#### 7.2 EuroQoL EQ-5D-5L

Questionnaires for the Health Economics analysis will include the EuroQoL EQ-5D-5L instrument. This is the most widely used tool for the collection and calculation of preference-based health related quality of life, and is required for the calculation of quality-adjusted life years (QALY). The EQ-5D is preferred in economic evaluations in health care (47, 48). The questionnaires will only be completed at the sponsor site (UHCW).

#### 7.3 Stool FIT

Samples with traces of haemoglobin in the faeces at and above the cut off value  $10\mu$ gHb/g are defined as suspected SBD. Any previous FIT results collected to triage patients can be sourced from patient records.

#### 7.4 Urine VOC

Duplicate samples are collected in universal sterilin pots (2/3rd full only) for each participant. These will be frozen at -80°c at sites and when ready transported to the central site on dry ice. Duplicate samples will be sent separately to avoid loss of samples. Thereafter samples will be sent for analysis on dry ice to the Manchester analytical lab and the UK National Measurement Laboratory. Once in the lab, they will be frozen until analysis. Records of the cold chain will be kept by individual and central sites up to transfer.

A subset of urine samples (n = 100) from the main recruiting site (UHCW NHS Trust) will be transferred directly to the National Measurement Laboratory (NML) in Middlesex for development of a standardised operating procedure for measurement in the future within accredited NHS laboratory networks.

The urine VOC analysis using established reference methods will be undertaken at the UK National Measurement Laboratory, Middlesex which is the national measurement laboratory for chemical and bio-measurement. Gas-chromatography mass spectroscopy system (GCMS) is considered the gold standard for VOC analysis and is commonly used to identify unknown chemicals. It comprises of a GC front-end, which separates complex mixtures of chemical based on their interaction with a retentive layer, resulting in chemical eluding out of the GC at different times (called the retention time). These individual chemicals are then ionised and the mass of the resultant fragments measured. As each chemical always fragments the same way, we can use these to identify specific chemicals. This will be used to validate the headspace sampling methods to be used and to provide an independent analysis of potential volatile biomarkers for the medical conditions of interest in this study. This will feed into subsequent "electronic nose" analysis.

IRAS 282247\_RECEDE protocol\_v2.2\_11.02.2022

The urinary volatiles will be analysed in Manchester using "electronic nose" techniques using an array of gas sensors coupled with an appropriate polymeric pre-concentrator. Appendix 3 provides a detailed description of the technique being utilised at Manchester for VOC analysis. This technique provides multivariate data documenting differences in the chemical composition of the urinary volatiles that may contain volatile biomarkers for a condition. This allows screening of populations rapidly using chemometric data analysis, neural networks and receiver operator curves to distinguish one population from another, with receiver operating curves being used to measure the appropriate thresholds to be set to distinguish samples as having colon cancer, colorectal adenomas, inflammatory bowel disease or microscopic colitis. Unlike GCMS – this technique does not provide identities of individual biomarkers but considers the data derived from the entire complex mixture of volatile chemicals that are present in urine headspace.

A receiver characteristic curve (ROC) with an area under the curve (AUC) of 0.63 or greater will be applied for the detection of SBD (colon cancer, colorectal adenomas or, inflammatory bowel disease). The threshold for participants samples being defined as having SBD will be >0.63 (see Appendix D).

To determine the relationship to the stool test (which is a quantitative continuous variable) a canonical correlation test will be applied. The canonical correlation tool is often used in a multivariate analysis of correlation. Canonical is the statistical term for analysing latent variables (which are not directly observed) that represent multiple variables (which are directly observed). Canonical correlation analysis is the analysis of multiple-X multiple-Y correlation. The canonical correlation coefficient measures the strength of association between two canonical variates. Canonical correlation analysis is preferable in analysing the strength of association between two constructs. This is because it creates an internal structure containing different importance of single item scores that make up the overall score.

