#### Evidence of stool FIT in SBD detection

Our previous data and that of others have shown that stool FIT on its own has sensitivities of 80%, 53% and 86% for colon cancer, adenomatous polyps and inflammatory bowel disease respectively (2, 11, 13). Importantly, the alternative stool marker faecal calprotectin (FCP) offers no added advantage for the added cost (2, 11). The sensitivity of FCP for colon cancer is lower at 68% (vs 80%) and 43% (vs 53%) for adenomatous polyps compared to FIT but comparable for diagnosis of inflammatory bowel disease (for which it is intended) (3). This has meant that NICE has not recommended FCP for diagnosis of SBD

IRAS 282247\_RECEDE protocol\_v2.2\_11.02.2022 Page **15** of **50** 

except inflammatory bowel disease. Note that blood or stool based genomic markers e.g. mSEPTIN 9, Cologuard (methylated DNA markers) whilst specific for CRC perform less well to identify colonic polyps (sensitivity 60% with specificity of 46%) (14). Moreover, these markers cannot identify other SBD such as inflammatory bowel disease. Their high cost (15) makes it prohibitive for routine use with almost comparable cost to that of a colonoscopy. Conversely, urine VOCs on their own can detect SBD with sensitivities for colon cancer, adenomatous polyps and inflammatory bowel disease at 80%, 92% and 86% respectively (6, 16),(17). Of further note, concordance between FIT and urine VOC is low to moderate indicating a potential synergistic effect when combining results from the two tests.

FIT (£18 per test) is recognised to be superior to the guaiac faecal occult blood test for detecting CRC due its ability to detect human haemoglobin (18). There is good evidence for its use within the screening population. In those with symptoms, there has been increasing evidence supporting its use in primary and secondary care. However, significant limitations as outlined earlier are the number of missed CRC cases, and lack of sensitivity and specificity to detect pre-malignant lesions (polyps) (6, 7, and 12). Thus, it is apparent that FIT on its own is not likely to be sufficient to detect SBD, but rather a second complementary test is required to improve SBD detection.

Existing evidence suggests that FIT on its own can miss up to 10% of CRC (applying threshold recommended by NICE), but adding urine VOC testing can reduce this to 3% (similar to colonoscopy) (6).

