We and others have studied VOC detection for CRC using different modalities – faeces, urine and breath (16, 27-29). The sensitivities range from 80-92% (95% CI: 63 to 94). More recently our group has also shown utility of urine VOC in CRC detection in those within the BCSP population (30). Our group has optimised methods for VOC detection in urine from sample collection, storage and stability as well as specific algorithm for analysis (6, 31, 32). This both allows for VOC analysis to be introduced into conventional secondary care laboratory setting and for its diagnostic utility to be optimised. We have already identified four potential key chemicals that are associated with CRC detection (cyclooctatetraene, propanediamine, methylbenzoic acid and isothiocyanate) (33) that contributes to 20 discriminant features providing a score that can be quantified and threshold adjusted accordingly – see Appendix A Table 1.

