#### 8 STATISTICS AND DATA ANALYSIS

8.1 Sample size calculation

To replace colonoscopy and CTC the new testing strategy requires very high sensitivity to avoid false negative results and missed disease. False positive results are also undesirable, but these participants would simply follow the colonoscopy testing pathway that all participants follow currently. Therefore, the sample size calculations are based on achieving acceptable sensitivity. There are some data on the utility of FIT alone and urine VOC alone in the detection of SBD(6, 10, 37). Our recent study (n=562) is the only published study that evaluated the combination of both FIT and urine VOC for the detection of colon cancer, which was 97% (95% CI: 90 to 100), similar to that for colonoscopy(6). The sensitivity of FIT alone in detecting IBD is 0.85, with the combined accuracy of FIT and VOC unknown. On the basis of these previous studies, and the necessity for high sensitivity to replace colonoscopy, we assumed that the sensitivity (Se) of the FIT and urine VOC tests to detect SBD would be at least 0.97 which is very near 1.0. The confidence interval for such high sensitivity has to be adjusted such that the interval does not exceed 1.0. One recommended method is to use the Zhou-Li method as described in equations 4.5 to

replaced by Se. Assuming that the sensitivity of FIT and VOC to be at least 97% then for Se = 0.97 and a 95% CI width of 0.05 (ensuring a high precision around the sensitivity estimate) the required number of participants with SBD is 200. Further assuming that the prevalence of SBD in the population with bowel symptoms is 19% (likely underestimate), then 1053 participants are required. Based on previous study(6) about 55% of the participants would return both stool and urine samples and sufficient for FIT and VOC analyses. Thus, the total sample size required is 1,915.

This strategy is robust to changes in the underlying assumptions of test accuracy. Confidence intervals for sensitivity for different observed sensitivity for 150, 200 and 250 cases of SBD are shown in Figure 5(a). For the target sensitivity of 0.97, the width of the confidence interval is 0.05 with 200 SBD participants, with narrower and wider confidence interval limits, when the observed sensitivity is above and below this value, respectively (Figure 5(b)).

Figure 5 Confidence intervals for different estimates of sensitivity for 150, 200 and 250 cases of SBD.

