#### 8.2.2 Primary outcome analysis

The primary outcome is diagnostic accuracy - sensitivity, specificity, NPV and PPV of the dual index test, FIT and VOC. A FIT result that is >10 µgHb/g faeces OR a VOC result with predicted probability >0.63 implies that the participant is defined as having SBD and need to be referred for colonoscopy. We will report 2x2 tables of test accuracy of the dual test by the reference standard (final report from the CTC or colonoscopy examination and confirmatory histology report of SBD which is either colon cancer, colorectal adenomas or inflammatory bowel disease), alongside summary measures of sensitivity, specificity, NPV and PPV, and their 95% confidence intervals. Confidence intervals for sensitivity and specificity estimates that are very close to 1.0 will be according to the Zhou-Li method and the intervals for NPV and PPV estimates that are very close to 1.0 will be according to the Bayesian method (38). These test accuracy estimates will be used in the economic model.

We will analyse the combined FIT+VOC test results as both parallel (results from both tests are interpreted in combination) and serial testing (VOC performed only if FIT negative, i.e. <10  $\mu$ gHb/g faeces). The "or" rule will be considered in the interpretation of both parallel and serial tests where the diagnosis is positive when either test is positive (FIT >10  $\mu$ gHb/g faeces and/or VOC predicted probability >0.63), and negative when both are negative (FIT <10  $\mu$ gHb/g faeces and VOC predicted probability <0.63). In the serial test, if the FIT is positive (FIT >10  $\mu$ gHb/g faeces) then the diagnosis is positive. Otherwise, use the result from VOC and if it is positive (VOC predicted probability >0.63) then the diagnosis is positive. If the VOC result is also negative then the diagnosis is negative. Mathematically, both methods would give the same diagnostic results but would make a difference in the economic model.

A 2x2 table of test accuracy for each individual index test by the reference test will also be presented. Sensitivity, specificity, PPV and NPV will also be presented with their 95% confidence intervals for FIT only and VOC only. Participants with missing data for either of the index tests (FIT or VOC) or the reference standard (colonoscopy) will be excluded from this analysis.

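### The canonical correlation test in section 7.4 does not suit a single FIT variable and, run over all participants, cannot tell overlap between FIT and VOC from their shared link to SBD (minor)

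*Protocol*

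**What the plan says.** Protocol section 7.4 (Urine VOC) describes the electronic-nose output: "This technique provides multivariate data documenting differences in the chemical composition of the urinary volatiles". It then fixes the method for relating VOC to FIT: "To determine the relationship to the stool test (which is a quantitative continuous variable) a canonical correlation test will be applied". The rest of that paragraph defends the choice, including: "Canonical correlation analysis is the analysis of multiple-X multiple-Y correlation". It does not name the VOC variables that enter, the scale for FIT, or whether the analysis is overall or within SBD status.

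Three other places bear on this:
- Section 8.2.2 uses one VOC quantity, a predicted probability with a cut-off: "A FIT result that is >10 µgHb/g faeces OR a VOC result with predicted probability >0.63 implies that the participant is defined as having SBD".
- Section 8.2.2 also plans the single-test results: "Sensitivity, specificity, PPV and NPV will also be presented with their 95% confidence intervals for FIT only and VOC only".
- Section 1.9, on earlier data, says: "concordance between FIT and urine VOC is low to moderate indicating a potential synergistic effect when combining results from the two tests".

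**The concern.** The method does not match the data it is applied to. Canonical correlation weights two sets of variables so that their combinations correlate as strongly as possible. With one FIT variable there is nothing to weight on that side.

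The VOC side can be read in two ways, and neither supports the stated rationale. If the multivariate sensor data enter, the VOC combination is the one closest to FIT, not the one trained to detect SBD and used in the primary rule. If the predicted probability enters, the analysis is a simple correlation.

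There is also an interpretive problem. Two tests that both respond to SBD are correlated across all participants even if they share nothing once SBD status is known. An overall coefficient therefore mixes the shared link to SBD with overlap between the tests given SBD. At stake is a supporting result that could be misread, not the primary analysis.

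**Working it through.** **The plan's own figures.** Section 8.1 gives: "a 95% CI width of 0.05 (ensuring a high precision around the sensitivity estimate) the required number of participants with SBD is 200". Then 200 / 0.19 = 1,052.6, so 1,053 analysable, and 1,053 / 0.55 = 1,914.5, so 1,915 recruited. These reproduce. The protocol states no figure for the canonical test itself.

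**Reduction to multiple correlation.** With one Y variable, the canonical correlation is the multiple correlation R of FIT on the q VOC variables. Its test is F = (R²/q) / [(1 − R²)/(n − q − 1)]. This is algebra.

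**Inputs.**
- n = 1,053 and prevalence p = 0.19 (8.1), so p(1 − p) = 0.1539.
- FIT sensitivity for SBD 0.63, since 37% of SBD was FIT-negative (1.9, Dual Testing). FIT sensitivity 0.80 and specificity 0.93 for CRC (Appendix D).
- FIT specificity for SBD is not given. I assume a range of 0.80 to 0.93.
- VOC AUC 0.67 for CRC (Appendix D), assumed to hold for SBD.
- Further assumptions: normal scales with equal variance, equal shifts across VOC variables, alpha 0.05, and FIT and VOC independent given SBD.

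**Induced correlation for one VOC score.** The VOC shift is dV = √2 × z(0.67) = 0.622, and the FIT shift is dF = z(sensitivity) + z(specificity). Then

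r = p(1 − p)·dF·dV / √[(1 + p(1 − p)dF²)(1 + p(1 − p)dV²)].

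For FIT 0.63/0.93, dF = 1.808 and r = 0.1731 / √(1.503 × 1.060) = 0.137. By the Fisher transformation, atanh(0.137) × √1,050 is about 4.47, so rejection is Φ(4.47 − 1.96), about 99%.

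**Simulated rejection, 1,000 runs per setting, all participants together:**

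| FIT sens/spec | dF | r, one score | q = 1 | q = 5 | q = 20 |
|---|---|---|---|---|---|
| 0.63/0.93 | 1.808 | 0.137 | 99% | 95% | 78% |
| 0.63/0.80 | 1.173 | 0.099 | 88% | 72% | 44% |
| 0.80/0.93 | 2.317 | 0.160 | 100% | 99% | 89% |

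The same test run within SBD status rejects 4.4% to 5.4% of the time in SBD and 4.1% to 5.6% in non-SBD, which is nominal.

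**Same correlation, different overlap.** Two large simulated populations (500,000 each) were given the same overall r of 0.136. VOC-positive was defined by a cut at the 63rd percentile of non-SBD.
- VOC independent of FIT given SBD: AUC rises from 0.900 (FIT) to 0.912 (FIT and VOC). Among FIT-negatives, 62% of SBD and 37% of non-SBD are VOC-positive.
- VOC dependent on FIT alone: AUC stays at 0.900. Among FIT-negatives, the figures are 40% and 36%.

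The overall coefficient does not separate the two. The FIT-negative proportions do.

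**Canonical variate against VOC score.** In an illustrative case, one VOC variable tracks SBD and another tracks FIT but not SBD. The canonical variate has r = 0.37 with FIT and AUC 0.56 for SBD. The SBD score has r = 0.14 and AUC 0.67. The two correlate only 0.37.

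**Size of the coefficient.** If 20 VOC variables unrelated to FIT entered, the expected R² would be 20/1,052 = 0.019, so R is about 0.14. The F test allows for this. The raw coefficient, if quoted as strength of association, does not.

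**The case against.** The strongest reply is that this is a descriptive analysis with a modest stated purpose, and much of that stands.

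- A reader might infer that the test is meant to show whether VOC adds to FIT. Section 7.4 says only that it concerns the relationship between the tests. Added value is judged from the accuracy tables in 8.2.2 and the ROC combinations in 8.2.3.
- A reader might take the 99% as a false-positive rate. It is not. In that model the overall association is real, so 99% is power. With VOC unrelated to both FIT and SBD, rejection is 4% to 5%.
- A reader might infer that the result would count against synergy and so point the wrong way. The synergy remark in 1.9 concerns the size of concordance, not significance. Mean coefficients of about 0.14 to 0.19 (1 to 20 variables, FIT 0.63/0.93) would read as low, so that harm is not shown.
- Analysis over all participants is the default reading, not a stated rule. The statistical analysis plan, which is not shown, could stratify.
- The maximisation argument needs several VOC variables to enter, which 7.4 does not say. The value 20 is illustrative. Section 1.9 says of the earlier identified chemicals that their pattern "contributes to 20 discriminant features providing a score", whereas the electronic nose does not identify compounds.

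The misfit itself is not answered by these points. The protocol names the method and argues for it, and FIT remains one variable however the details are later filled in.

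**Conclusion.** The point holds in limited form, and its severity is minor. Section 7.4 fixes a method whose rationale does not fit a single FIT measurement. Depending on the VOC input, it yields either a quantity that is not the score used in the primary rule or an ordinary correlation. Unless conditioned on SBD, it cannot say whether the tests overlap given disease status: rejection is 44% to 100% over the assumed ranges with no such overlap present.

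These figures rest on a normal latent scale, equal VOC shifts, alpha 0.05, and CRC values for VOC AUC and in part for FIT accuracy. The lower the FIT specificity assumed for SBD, the weaker the effect. No primary estimate, sample size or economic input depends on this test.

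**What to change.** In section 7.4, replace the canonical correlation paragraph with the following:
- The Spearman correlation, with 95% CI, between FIT concentration and the VOC predicted probability of 8.2.2, reported separately in participants with and without SBD. Present it as a descriptive measure of overlap and not as a test of added value, since a pure-noise VOC score would also give a value near zero.
- The proportion VOC-positive among FIT-negatives, with 95% CI, separately with and without SBD. It follows from the 8.2.2 tables under the either-positive rule: (dual TP − FIT TP) / FIT FN in SBD, and (dual FP − FIT FP) / FIT TN in non-SBD, in the same complete cases.

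This is a wording change and needs no new data. The cost is precision. For a correlation near zero, the approximate half-width 1.96/√(n − 3) is 0.14 in 200 SBD cases and 0.07 in 853 without SBD, against 0.06 in all 1,053. If 37% of 200 SBD cases are FIT-negative, the VOC-positive proportion rests on 74 people, with a half-width of about 11 percentage points at 50% (1.96 × √(0.25/74) = 0.114).
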